The influence of daily grapes' intake on sarcopenia in postmenopausal women

1) Protocol Title

The influence of daily grapes' intake on sarcopenia in postmenopausal women

Protocol Version Date:

This is a new IRB submission

2) Objectives

The objective of this project is to evaluate whether the daily consumption of a freeze-dried table grape powder, rich in phenolic compounds, mitigates sarcopenia in postmenopausal women. To achieve this objective, we will pursue the following aims:

1. To determine the efficacy of a freeze-dried table grape powder, rich in phenolic compounds, to mitigate sarcopenia parameters in postmenopausal women.
1. To evaluate the effect of a freeze-dried table grape powder on key metabolic regulators of sarcopenia in postmenopausal women, specially irisin.

We hypothesize that daily dietary supplementation with a grape powder improves health span, mitigates sarcopenia parameters and increases irisin plasma levels in postmenopausal women.

[figure not shown]
The successful completion of this pilot human study will provide evidence on the benefit of the daily addition of table grape to the diet of healthy older women to improve sarcopenia by regulating some key metabolic regulators. This will provide strong preliminary results to apply for competitive grant (USDA) in order to expand these findings using a bigger sample size, multiple doses and various time-periods.

3) Background

As stated above, sarcopenia is defined as a loss of muscle strength and mass in older individuals. However, until recently, there has been no widely accepted definition of

sarcopenia that was suitable for use in research and clinical. Sarcopenia leads to fragility and disability, worsens the prognosis of many diseases, and significantly enhances morbidity and mortality. Furthermore, a higher risk of death from all causes compared with non-sarcopenic subjects was found in > 60 years old and mainly in > 80 years old (13, 14). With the increasing life expectancy and rapid growth of the aged population, sarcopenia is becoming an emerging public health issue with huge socioeconomic burden.

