- 24-hs food and physical activity questionnaire
- Seated resting blood pressure will be measured.
- Weight will be measured.
- Subjects will take the assigned supplement.
- Venous blood samples will be collected (20 ml).
- A hematocrit will be performed in order to discard anemia.
- Snack will be provided to the participants.
- Hand grip strength and SPPB test will be completed.
- Unused and empty packages of the study product will be return.

10) Study Timelines

Duration of individual subject's participation will be ~6 weeks. The study will include: 1 visit (visit 0) for the screening process that will last approximately 2 h and 3 more visits (visits 1, 2 and 3) for intervention process that will last approximately 2 h each. Visit 0 will involve an in-person screening to obtain written informed consent and determine if subjects meet the inclusion/exclusion criteria. Visit 1, 2 and 3 (at 0, 3 weeks and at the end of the 6 weeks, respectively) will include blood sample collection and tests performance.

11) Study Endpoints

Primary endpoint:

Hand-grip strength media value of 16 kg or lower

Secondary endpoints:

Levels of Irisin as a marker of sarcopenia

Glucose, Insulin, GLP-1, GLP-2, GIP, Adiponectin, leptin and ghrelin, Blood urea nitrogen, creatinine, Aspartate transaminase, Alanine transaminase, Total cholesterol, triglyceride, high-density lipoprotein (HDL), low-density lipoprotein, IL-6, IL-15, 25-hydroxyvitamin D as markers of general metabolism state.

12) Data and/or Specimen Management and Confidentiality

Data management: The de-identified data will be analyzed for statistical significance with the help of the Biostatistics group at UC Davis, including univariate graphical, analytic summaries and bivariate relationships using box plots, scatter plots, and correlations. To compare participants in the two diet groups (Placebo control and freeze-dried table grape powder) a paired Student's t test (two-tailed) will be used. Data involving more than two repeated measures, such as grip strength tasks, or irisin levels, will be assessed by repeated measures (ANOVA). Differences will be considered significant at $P < 0.05$. Significant results will be also subjected to analysis of covariance (ANCOVA) to account for group differences at baseline and post hoc comparisons using the Bonferroni correction.

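### One P < 0.05 rule covers 21 outcomes; the Bonferroni step works within an outcome, so a false significant difference somewhere has about a 66% chance if outcomes are independent (about 41% in the favourable direction)

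*Protocol*

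**What the plan says.** Section 11 of the protocol gives hand-grip strength as the primary endpoint. The secondary endpoints are irisin ("Levels of Irisin as a marker of sarcopenia") and a list that runs "Glucose, Insulin, GLP-1, GLP-2, GIP, Adiponectin, leptin and ghrelin, Blood urea nitrogen, creatinine, Aspartate transaminase, Alanine transaminase, Total cholesterol" and goes on to triglyceride, HDL, LDL, IL-6, IL-15 and 25-hydroxyvitamin D. The markers in that list are described as reflecting general metabolic state.

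Section 12 gives the analysis. For the comparison of the two arms, "a paired Student's t test (two-tailed) will be used". Data with more than two repeated measures go to repeated-measures ANOVA, with grip and irisin as the examples. One threshold then follows: "Differences will be considered significant at $P < 0.05". Results that pass it are taken on to ANCOVA and to "post hoc comparisons using the Bonferroni correction".

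Section 4 bases the sample size on change in plasma irisin, which it calls the primary outcome, and enrols 7 per group, 14 in total. Section 2 says that the completed pilot "will provide evidence on the benefit of the daily addition of table grape" and will supply preliminary results for a competitive grant.

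**The concern.** The threshold in section 12 applies equally to all outcomes. Section 11 ranks the endpoints by label, but section 12 does not turn that ranking into a testing order, and it does not say that a secondary marker below 0.05 is only a lead for later work. The one correction named starts after an outcome has already passed 0.05. It most naturally adjusts between-visit comparisons inside that outcome, and nothing in the text extends it across the 21.

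The usual answer is that one primary test is protected and the rest are supportive. That is weakened here because sections 4 and 11 name different primaries, so a reader cannot tell which test is the protected one.

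What is at stake is how an isolated marker result is read. Under the stated rule, one blood marker at P = 0.04 in 14 women is a significant finding and can be cited for the benefit that section 2 anticipates.

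**Working it through.** **Inputs from the protocol**
- Threshold: 0.05, two-tailed (section 12), which is 0.025 in the favourable direction.
- Outcomes (section 11): 13 markers from glucose to total cholesterol, plus 6 from triglyceride to 25-hydroxyvitamin D, make 19. Adding irisin and grip gives 21.
- Arm size: 7 (section 4).

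The protocol states no error rate across outcomes, so there is no figure of its own to reproduce.

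**Assumptions**
- The powder has no effect on any outcome.
- Correlation between outcomes is not given, so it is shown over a range, taken as equal for all pairs.
- A two-sample t-test is used because the arms are parallel. The word *paired* in section 12 is a separate matter.

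**Step 1: one test per outcome**
- Expected false positives: 21 × 0.05 = 1.05, whatever the correlation.
- At least one false difference, either direction, independent outcomes: 1 − 0.95^21 = 0.659.
- At least one false result in the favourable direction, independent outcomes: 1 − 0.975^21 = 0.412.

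**Step 2: correlated outcomes** (40,000 simulated null trials per value, 7 per arm; the favourable sign alternates across outcomes)

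| Assumed correlation | Either direction | Favourable direction |
|---|---|---|
| 0 (formula) | 66% | 41% |
| 0.2 | 62% | 40% |
| 0.3 | 57% | 37% |
| 0.4 | 51% | 34% |
| 0.5 | 45% | 31% |
| 0.8 | 25% | 19% |

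The either-direction chance falls below one half once the common correlation goes a little above 0.4.

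**Step 3: the planned ANOVA and Bonferroni steps.** All blood markers are measured at visits 1, 2 and 3, so the repeated-measures route can apply to all of them. Two further assumptions are needed: the group-by-visit term is the one tested, and the between-visit correlation is 0.7. Results for 21 independent outcomes, either direction:
- ANOVA at 0.05, then Bonferroni on the week 3 and week 6 changes: about 3% per outcome, 47% over 21 (27% in the favourable direction).
- Bonferroni on the two changes without the ANOVA gate: about 64%.
- ANOVA alone: about 66%.

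So the within-outcome steps bring the chance to between 47% and 66%, depending on how they are applied. None of them brings it near 5%.

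**Step 4: the two candidate primaries alone.** Grip and irisin, each tested at 0.05: 1 − 0.95^2 = 9.75% if independent, and 1 − 0.975^2 = 4.9% in the favourable direction.

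**The case against.** **Primary and secondary labels exist.** Section 11 does separate the endpoints, and its description of the 19 markers suggests a descriptive role. It would be wrong to say that the protocol has no order at all. What stands is narrower: the P < 0.05 rule ignores that order, and section 4 contradicts it.

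**This is a pilot, and a statistical analysis plan may exist.** Unadjusted secondary tests are commonly accepted in a 14-person pilot, and labelling them exploratory is often left to the analysis plan. This is the strongest objection, and it limits the point to how results are labelled and claimed. It does not remove the point, because the protocol is not silent here. It states a decision rule, and section 2 expects evidence of benefit.

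**Stronger readings that do not hold.** A reader might infer that a false *benefit* is more likely than not. It is not: the 66% counts differences in either direction, and the favourable-direction chance is 41% at independence and lower with correlation. For some markers, such as urea nitrogen and creatinine, no favourable direction is stated.

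A reader might also treat weeks 3 and 6 as two unadjusted tests per outcome, which gives about 9% per outcome and 87% over 21 independent outcomes. That ignores the repeated-measures ANOVA and the Bonferroni step that section 12 plans, so the figure should not be used.

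Finally, related markers (lipids, liver enzymes, incretin hormones) are likely to be correlated, which pulls all the figures down. The range in the table allows for that.

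**Conclusion.** The point holds as a matter of how significance is declared across outcomes. The count of 21 is firm, as is the expectation of 1.05 false positives on one test per outcome. The size of the familywise risk rests on a correlation that the protocol does not give. Over the range 0 to 0.5 it is 66% to 45% in either direction and 41% to 31% in the favourable direction. With the planned within-outcome steps modelled, it is 47% to 66% in either direction for independent outcomes.

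The documents support saying that an isolated marker below 0.05 is weak evidence under this rule. They do not support saying that the trial will probably show a false benefit. The protocol should be changed, but the defect lies in its wording and does not affect the data to be collected.

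**What to change.** Replace the blanket significance sentence in section 12 with the following:

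1. Reconcile sections 4 and 11 so that one outcome, chosen by the sponsor, is primary, and test it at two-sided 0.05 at week 6.
2. Test the other of grip and irisin at 0.05 only if the first is significant (fixed sequence).
3. Report the 19 metabolic markers as exploratory, with between-arm differences and 95% confidence intervals and no claim of significance. If a formal statement is wanted, apply Benjamini-Hochberg across the 19.
4. Keep the existing Bonferroni adjustment for between-visit post hoc comparisons, and say that this is its scope.

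The cost is a few lines of wording and no extra data. The downside is that fewer markers can be called significant in the grant application.

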levels compared to control and high fat diet groups (**Figure 2A-B**). Furthermore, supplementation with GPE led to the increase in irisin plasma level (**Figure 2C**)(11).

In order to understand the underlying mechanism involved in the GPE-related irisin increased levels, we next evaluated the effects of epicatechin, one of the main flavonoids present in GPE, in L6 myotubes challenged with palmitate, to mimic a condition of fatty acids oversupply. Protein levels of PGC- 1 α and FNDC5 were significantly higher in the EC and palmitate-treated cells, compared with palmitate-treated cells (**Figure 3A-B**). The same tendency was observed by immunocytochemical analysis of PGC-1 α , while no differences were observed in FNDC5 fluorescence intensity among treatments (**Figure 3D-E**). In addition, EC induced a 2-fold increase in irisin levels secreted to the medium compared with cells treated with only palmitate (**Figure 3C**). These data strongly indicate that phenolic compounds enhance irisin levels in vitro and in vivo.

These intriguing data allow us to hypothesize that phenolic compounds present in grapes might have a positive effect in human health, specially preventing sarcopenia in elderly humans, in part, by increasing irisin levels.

4) Enrollment Numbers

We chose the “changes in plasma irisin levels” as our primary outcome to determine the power calculations for sample size. Based on our preliminary data (11), 5 individuals per group are required to reach 80% power to detect differences in irisin levels between the groups, at a $\alpha=0.05$, using a two-sided paired T-test. We propose to enroll 7 individuals per group, instead of 5, in the event of a patient drop out of the study (for any unforeseen circumstances). In total we will have 14 subjects.

5) Inclusion and Exclusion Criteria

Inclusion Criteria: postmenopausal women aged 60 years or older with a hand-grip strength media value of 16 kg or lower, normal body mass index (BMI) with values between 18.4 and 24.9 kg/m², blood pressure below 130/80 mmHg, and plasma glucose and cholesterol concentrations below 100 and 200 mg/dl.

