Return stool and urine collection kit			X	X
Adverse events assessment			X	X

After confirmation of the inclusion/exclusion criteria enrolled subjects will be asked to travel to Ragle Human Nutrition Center at University of California Davis for 3 study visits: a baseline visit (**visit 1**), and a 3-week intervention visit (**visit 2**) and a final 6-week visit (**visit 3**)

Visit 1 (baseline visit):

On this visit, baseline measurement will be done. Fasted participants (12 h) will provide blood samples and complete two tests:

Blood samples: from each participant 20 ml of blood will be extracted. The following parameters will be measured in plasma, (the same parameters will be measure in the following visits 2 and 3):

Blood parameter	Volume of blood needed	Visit 1	Visit 2	Visit 3
Irisin	1200 ul	X	X	X
Glucose	1000 ul	X	X	X
Insulin	1200 ul	X	X	X
GLP-1/ 2, GIP	2000 ul	X	X	X
Adiponectin, leptin and ghrelin	3000 ul	X	X	X
Blood urea nitrogen, creatinine	1000 ul	X	X	X
Total cholesterol, triglyceride, high-density lipoprotein (HDL), low-density lipoprotein	2000 ul	X	X	X
Aspartate transaminase, Alanine transaminase	2000 ul	X	X	X
IL-6, IL-15	2000 ul	X	X	X
25-hydroxyvitamin D	1000 ul	X	X	X
Hematocrit	500 ul	X	X	X

Total volume of blood per visit	~ 20 ml	20 ml	20 ml	20 ml
---------------------------------	---------	-------	-------	-------

After taking the blood samples a snack will be provided to the participants in order to complete the following tests.

1. Hand-grip strength: previously described in the screening point
2. Short Physical Performance Battery (SPPB): the SPPB score will be based on three tests, as follows: balance test, gait speed test, and chair stand test (see **Attachment E**). Of note, these tests have been used as a predictive tool for possible disability and can aid in the monitoring of function in older people.

Following, the subjects will randomize into the study supplement: a) Placebo powder (46 g placebo powder in 180 ml of water); or b) freeze-dried table grape powder (46 g grape powder in 180 ml of water). The supplement will be supplied to the participants to complete the following 3 weeks supplementation until the next visit. The investigator or designee will explain the details regarding the preparation and consumption of the supplement [a dosing protocol will be uploaded too (**Attachment F**)].

Also a 24-hs food and physical activity questionnaire will be performed

Briefly, at visit 1:

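### Section 12 runs baseline-adjusted ANCOVA only on results that are already significant and does not say which P value decides

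*Protocol*

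**What the plan says.** Section 12 (Data and/or Specimen Management and Confidentiality) sets out the analysis in three steps.

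- For the two-arm comparison, "a paired Student's t test (two-tailed) will be used".
- For outcomes with several visits: "Data involving more than two repeated measures, such as grip strength tasks, or irisin levels, will be assessed by repeated measures (ANOVA").
- After setting the threshold at P < 0.05: "Significant results will be also subjected to analysis of covariance (ANCOVA) to account for group differences at baseline", followed by Bonferroni-corrected post hoc comparisons.

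Neither of the first two steps names a baseline covariate. An outcome that is not significant at that stage gets no ANCOVA. The section does not say whether the earlier P value or the ANCOVA P value carries the conclusion.

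Baseline data are complete by design. Section 9 lists the plasma markers for visit 1 and adds that "the same parameters will be measure in the following visits 2 and 3"; grip strength is also scheduled at all three visits. Every endpoint in Section 11 (grip, irisin and 19 further markers) therefore has a visit-1 value.

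Section 4 plans 7 women per arm, 14 in all, on the basis that "5 individuals per group are required to reach 80% power to detect differences in irisin levels between the groups". Section 2 says that this pilot is meant to supply preliminary results for a grant to fund a larger study.

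**The concern.** A covariate adjustment should be chosen before the data are seen and applied to every outcome of the same kind. Here it is chosen by the data, and two things follow.

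1. **The decision rule is open.** An outcome that passes the first test has two P values. The text can mean that both must be below 0.05, or that ANCOVA is a supporting check. The first reading lowers power and makes the rule conservative. The second keeps the error rate near 5% but leaves the conclusion unsettled whenever the two disagree.
2. **Adjusted estimates are selected.** They will exist only for outcomes that were significant, and such estimates are too large on average. A pilot is read mainly for its estimates. If these ones are used to plan the larger study, that study may be too small.

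This is not a claim that baseline imbalance goes uncorrected for grip and irisin. The group-by-time term of a repeated-measures ANOVA already uses the visit-1 value, so a constant difference between arms cancels.

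**Working it through.** **Inputs from the protocol.** 7 per arm, three visits (0, 3 and 6 weeks), two-sided 0.05, first-stage test without a baseline covariate, ANCOVA only if that test is significant.

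**Inputs assumed.** The protocol gives no effect size, SD or between-visit correlation. SD is set to 1, the correlation ρ between any two visits to 0.5, 0.7 or 0.8, and the week-6 effect to 0, 0.5, 1, 1.5 or 2.02 SD, with half of it present at week 3 unless stated.

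**The plan's own figure.** Five per group cannot be reproduced without an effect size. Solving the noncentral t for 80% power gives the effect it implies:

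- independent groups: noncentrality d√(5/2) on 8 df, so d = 2.02 SD;
- paired: noncentrality d_z√5 on 4 df, so d_z = 1.68 SD of the differences.

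**Why the choice of analysis matters.** Per subject, the variance behind the week-6 comparison is 1 for follow-up values, 2(1−ρ) for change, and 1−ρ² for ANCOVA. At ρ = 0.5 these are 1, 1.00 and 0.75; at 0.7 they are 1, 0.60 and 0.51; at 0.8 they are 1, 0.40 and 0.36. ANCOVA is lowest each time, at a cost of one residual degree of freedom (11 instead of 12).

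**Simulation.** 40,000 trials per setting (60,000 for the conditional estimates). The first stage is the group-by-time F test on (3−1) = 2 and (14−2)(3−1) = 24 df. ANCOVA regresses week 6 on arm and visit 1, with 14−3 = 11 residual df. Rejection rates in %, for ρ = 0.5 / 0.7 / 0.8:

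| Week-6 effect | ANCOVA on every outcome | Repeated measures alone | Both required |
|---|---|---|---|
| 0 | about 5 | 5.0 / 5.0 / 4.9 | 1.7 / 1.8 / 1.9 |
| 1 SD | 47.2 / 62.6 / 77.8 | 33.2 / 51.4 / 70.2 | 27.7 / 46.0 / 65.9 |
| 1.5 SD | 80.3 / 92.6 / 98.1 | 64.8 / 87.0 / 97.1 | 61.1 / 85.0 / 96.2 |
| 2.02 SD | 96.1 / 99.4 / 99.9 | 89.4 / 98.9 / 100 | 88.1 / 98.6 / 99.9 |

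*Loss if both are required* (column 2 minus column 4): 20 / 17 / 12 points at 1 SD, 19 / 8 / 2 at 1.5 SD, 8 / 1 / 0 at 2.02 SD.

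*Loss if repeated measures decides* (column 2 minus column 3): 14 / 11 / 8, 16 / 6 / 1 and 7 / 1 / 0 points.

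*Disagreement*, as the share of first-stage significant outcomes in which ANCOVA is not significant: at 1 SD and ρ = 0.5, (33.2 − 27.7)/33.2 = 17%. Across ρ it is 17 / 11 / 6% at 1 SD, 6 / 2 / 1% at 1.5 SD and 67 / 63 / 62% under the null.

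*Mean ANCOVA estimate among outcomes that pass the first stage:*

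| True effect | Mean estimate (SD) |
|---|---|
| 0.5 SD | 1.01 / 0.94 / 0.85 |
| 1 SD | 1.39 / 1.24 / 1.14 |
| 1.5 SD | 1.70 / 1.58 / 1.52 |
| 2.02 SD | 2.09 / 2.03 / 2.02 |

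Run on every outcome, ANCOVA is unbiased.

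**Sensitivity to the time course.** With the full 1 SD already present at week 3, ANCOVA has 47.6 / 63.1 / 77.5% power, repeated measures 42.6 / 64.8 / 82.4% and both together 30.5 / 51.7 / 71.4%. Requiring both then loses 17 / 11 / 6 points. Repeated measures alone loses 5 points at ρ = 0.5 but gains 2 and 5 points at 0.7 and 0.8.

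**Sensitivity to the first-stage test.** A separate simulation (100,000 trials per setting) used an unpaired t test as the first stage, because the arms are independent. At 1 SD, requiring both loses 12.6 / 27.0 / 39.9 points if the t test is on follow-up values and 12.7 / 8.6 / 5.0 if it is on change. The null rate for both is 2.6 / 1.8 / 1.3% and 2.7 / 3.0 / 3.4%. At ρ = 0.5 the mean adjusted estimate among passers is about 1.35 SD in either case.

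**The case against.** **The natural reading is that the first test decides.** Results are called significant before ANCOVA is mentioned, and no sentence demands that both tests succeed. This is fair: the both-required figures describe one possible reading, and on the other the error rate stays near 5%. But the text does not settle it, and a supporting analysis that contradicts 6 to 17% of significant results at 1 SD needs a stated role. Nor can this be left to an SAP, because the protocol itself fixes the conditional rule.

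**If repeated measures governs, the conditional rule does not cause the power loss.** It comes from comparing a 2-df test with a 1-df week-6 ANCOVA, and it reverses for an early effect with high correlation. This stands. Lost efficiency is a possible consequence of the plan, not a certain one, and the remedy should allow a model that uses week 3.

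**The inflation is ordinary selection on significance.** Among outcomes significant by ANCOVA itself, the mean estimate at 1 SD would be 1.37 / 1.21 / 1.12, almost the same. That is true, and it is why the remedy is to report every adjusted estimate. The plan also promises descriptive summaries that are not limited to significant outcomes, and it does not say that adjusted estimates will size the next study. The undersizing risk is therefore plausible rather than stated.

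**Near the effect implied by the sample size, little is lost.** This is correct at about 2 SD. The larger figures need smaller true effects, which the protocol neither states nor excludes.

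**Conclusion.** The point holds. Section 12 makes baseline adjustment depend on an earlier significant result, names no governing P value, and so yields adjusted estimates only for a selected set of outcomes. These three facts rest on the text alone.

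The size rests on assumed effects, correlations and time course. At a true 1 SD, adjusted estimates are overstated by 14 to 39%. Power lost against ANCOVA on every outcome is 12 to 20 points if both tests are required. If repeated measures decides, it ranges from an 8 to 14 point loss with a gradual effect to a gain of up to 5 points with an early effect and high correlation. At about 2 SD and correlation 0.7 or more, both costs nearly vanish. The null rate of about 2% when both are required is specific to the repeated-measures first stage; with a t test first it ranges from 1.3 to 3.4%. No reading inflates type I error. The change should be made because it is cheap and removes the ambiguity, but the fault does not invalidate the trial.

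**What to change.** Replace the conditional sentence in Section 12 with one along these lines: *Every continuous outcome will be compared between arms by ANCOVA of the visit-3 value on arm and the visit-1 value, whether or not any unadjusted result is significant; this result governs.*

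If an effect by week 3 is expected, name instead a mixed model with arm, visit, arm-by-visit and baseline. Choose one of the two in advance.

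In either case, report the adjusted difference with its 95% CI for every outcome, label unadjusted tests as descriptive, and keep Bonferroni for post hoc visit contrasts.

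The cost is one or two sentences and no new data. ANCOVA uses one residual degree of freedom (11 instead of 12). At a correlation near 0.3 it has no advantage over an independent week-6 t test (40.5% against 40.7% power at 1 SD).
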